##### **Screening visit:**

- Obtain and document signed Informed Consent document and HIPAA Authorization
- Review past medical history to verify the inclusion/exclusion criteria
- Collect date of birth, age, gender, contact information, DoD ID number, name of standard of care medications (over-the-counter and prescription)
- Women of child bearing potential will be reminded that they only reliable methods of birth control are total abstinence or surgical removal of the uterus. Other methods, such as the use of condoms, a diaphragm or cervical cap, birth control pills, intrauterine device (IUD), or sperm-killing products are not totally effective in preventing pregnancy. They will be asked to alert study staff if they become pregnant or feel that they might be pregnant.

**Randomization:** Subjects will be randomized using a random number generator using simple randomization into 1 of 3 research treatment groups, with approximately 13 subjects in each arm:

Group 1: Auricular semi-permanent (ASP gold) needles

Group 2: Intradermal (long) needles using J-type No. 1 (.16) x 15mm

Group 3: Pylonex Pink 1.5mm (0.2 x 1.5mm)

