### **9.4 Study Design:**

Describe study design in one to two sentences (e.g., prospective, use of existing records/data /specimens, observational, cross-sectional, interventional, randomized, placebo-controlled, cohort, etc.). Specify the phase – Phase I, II, III, or IV – for FDA-regulated investigational drug research

Randomized clinical trial comparing ASP, long, and pyonex needles by recruiting and treating 13 patients per group with the goal of analyzing at least 10 patients' questionnaires per group comparatively for effect and tolerance of different BFA needles.

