## 11.2 Sample Size:

A priori power analysis was performed using the DVPRS variable as described below. The analysis indicates a minimum of 10 subjects in each needle group, for a total sample size of 30, will have a power of 0.44 to detect the minimal clinically important difference at alpha = 0.14. We will be recruiting a total of 39 subjects, which is inclusive of a 30% drop out rate to accommodate those that may be lost to the study or have missing data to achieve a final total of 30 subjects.

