## 11.4 If you are recruiting by study arm, please identify the arms of the study and how many subjects will be enrolled in each arm

Randomization: Subjects will be randomized using a random number generator using simple randomization into 1 of 3 research treatment groups, with approximately 13 subjects in each arm:  
 Group 1: Auricular semi-permanent (ASP gold) needles  
 Group 2: Intradermal (long) needles using J-type No. 2 (.18)x 15mm  
 Group 3: Pyonex Pink 1.5mm (0.2 x 1.5mm)

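### Simple randomization of 39 subjects does not hold 13 per needle group, and in about one trial in three leaves some arm below the stated minimum of 10 before any dropout

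*Combined protocol and SAP*

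**What the plan says.** The randomization paragraph of section 10.1 assigns subjects with a random number generator, "using simple randomization into 1 of 3 research treatment groups, with approximately 13 subjects in each arm". Section 11.4 repeats the method and the target, "with approximately 13 subjects in each arm".

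Other sections treat the arm sizes as features of the design:

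- Section 9.4 describes the trial as "recruiting and treating 13 patients per group with the goal of analyzing at least 10" questionnaires per group, without the word approximately.
- Section 11.2 rests the power statement on "a minimum of 10 subjects in each needle group, for a total sample size of 30".
- Section 11.2 also sets recruitment: "We will be recruiting a total of 39 subjects, which is inclusive of a 30% drop out rate". The Goals in section 9.3 give the same total and the same 10 per group.
- Section 11.1 excludes subjects with missing data, so every incomplete record makes its arm smaller.

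The documents state no block size, cap on arm size, minimization scheme or replacement rule.

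**The concern.** Under simple randomization each assignment is independent of those before it, so arm sizes are random. The plan recruits three subjects per arm beyond the minimum of 10, and sections 9.3 and 11.2 reserve that margin for loss to follow-up and missing data. If the allocation itself produces arms of 9 or 10, the margin is gone before the first subject is lost.

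Both hypotheses in section 9.3 compare needles, as do H01 and H03 in section 11.1. The tolerance outcomes are 5-point scales tested by chi-squared or Fisher's exact test, and those tables are already sparse at 10 per arm. An arm that starts below 10 cannot meet the plan's own minimum however complete the follow-up.

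**Working it through.** **Inputs**

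- Total recruited N = 39; minimum 10 per group, 30 in all (section 11.2).
- Target 13 per group (section 9.4).
- Simple randomization to three arms (sections 10.1 and 11.4).
- Allocation probability 1/3 per arm. This is an assumption: equal targets imply it, but no ratio is stated.

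**The plan's own figures**

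- *Recruitment.* 30 × 1.3 = 39. Losing 9 of 39 is 23.1%, so the margin covers 23% loss. A 30% loss would need 30/0.7 = 42.9, that is 43. This is a separate matter, but it sets which loss rate is relevant below.
- *Power.* Section 11.5 gives mean 4.4, SD 2.4 and a 25% difference: 0.25 × 4.4 = 1.1 points, d = 1.1/2.4 = 0.458, f = d/2 = 0.229. For the between-group test of a repeated-measures ANOVA with m = 4 measurements and correlation ρ = 0.5 (assumed; the plan gives none), λ = f²·N·m/[1 + (m − 1)ρ] = 0.0525 × 30 × 4/2.5 = 2.52. With F(2, 27) at alpha 0.14, power is 0.442 against the stated 0.44.

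**Arm sizes at randomization**

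P(a, b, c) = 39!/(a! b! c!) × (1/3)³⁹ with a + b + c = 39, summed exactly. One million simulated trials gave the same 0.340 for the fourth row.

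| Event | Probability |
|---|---|
| Exactly 13/13/13 | 0.021 |
| All arms 12 to 14 | 0.137 |
| All arms 11 to 15 | 0.330 |
| At least one arm below 10 | 0.340 |
| One named arm below 10, Binomial(39, 1/3) ≤ 9 | 0.115 |

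The expected smallest arm is 10.0 and the expected largest 16.1.

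**Arm sizes after loss**

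Loss is assumed independent, with the same rate q in every arm. An arm of size n keeps Binomial(n, 1 − q) subjects. With arms fixed at 13, P(some arm below 10) = 1 − [1 − P(Binomial(13, 1 − q) ≤ 9)]³. At q = 0.10 the inner probability is 0.034, giving 1 − 0.966³ = 0.10. Under simple randomization the same calculation is averaged over the multinomial.

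| Loss | Simple | Fixed 13/13/13 |
|---|---|---|
| 10% | 0.62 | 0.10 |
| 23.1% (9 of 39) | 0.92 | 0.73 |
| 30% | 0.98 | 0.93 |

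**Effect on precision**

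The standard error of a pairwise difference is proportional to √(1/n₁ + 1/n₂).

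- 13 v 13: √(2/13) = 0.392.
- 10 v 16: √(1/10 + 1/16) = 0.403, or 2.8% larger.
- 9 v 15: √(1/9 + 1/15) = 0.422, or 7.5% larger.
- Average over simple randomization of 39: 2.7% larger.

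With 30 completers, the power model above and one needle differing from the other two, average power is 0.432 under simple allocation against 0.442 at 10/10/10.

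**Behaviour of blocks**

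- Blocks of 3 end at 13/13/13 at subject 39.
- A block of 6 begun at subject 37 is cut after three subjects. Those three come from three different arms with probability 2·2·2/C(6,3) = 8/20 = 0.40; otherwise the arms end 12/13/14.
- If sizes 3 and 6 are drawn with equal probability, such a block straddles subject 39 in about one list in three. Exactly 13/13/13 then results in 1 − (1/3)(0.60) = 0.80 of lists.
- No arm is below 12 at 39 in any of these cases.

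**The case against.** The strongest reply is that little is lost. The sections that describe randomization say approximately 13, section 9.4 calls 10 analysed a goal, and the trial is a pilot with stated power of 0.44 at alpha 0.14. Nothing abrupt happens between 9 and 10 subjects, and an average rise of 2.7% in a standard error is minor. That stands as far as precision goes, and a reader who infers a serious loss of power would be wrong. It does not reconcile the sections, however. Even reading approximately as 11 to 15, only a third of trials qualify, and the minimum of 10 is the plan's own.

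A second reply is that dropout dominates. It is largely right: at the 23% loss that recruiting 39 allows for, balanced arms still leave some arm short in 73% of trials. The large contrast, 62% against 10%, needs 10% loss, a rate the documents do not give.

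Third, simple randomization has one real merit in an unblinded trial: the next assignment cannot be predicted. Blocking gives up some of that.

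Two stronger readings should be resisted. The 34% is for any arm; the Pyonex arm, on which hypothesis 2 rests, starts below 10 in 11.5% of trials. A reader might also infer that needle becomes confounded with calendar period as arm sizes drift during enrolment. The documents describe no enrolment period, operator change or seasonal effect, and simple randomization leaves assignment independent of time in expectation.

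**Conclusion.** The point holds as a mismatch between the allocation method and the arm sizes the plan relies on. The probabilities at randomization are exact, given 39 subjects and equal allocation. The figures after loss also assume independent loss at the same rate in every arm, and the power comparison assumes a correlation of 0.5.

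The consequence is moderate: the dropout margin is spent on chance imbalance, and the stated per-group minimum is left unprotected. The documents do not support a claim that the comparison is biased or invalid, or that balanced allocation alone would secure 10 analysed per arm. The change is worth making because it is cheap and removes the avoidable part of the shortfall.

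**What to change.** In sections 10.1 and 11.4, replace simple randomization with a computer-generated 1:1:1 permuted-block list, using blocks of 3 and 6 in random order and built to end at exactly 39, so that each arm receives 13. Fix the length explicitly; a list cut at 39 without that condition can end 12/13/14. Conceal the next assignment from the staff who enrol, for example in sealed opaque envelopes.

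The cost is one sentence in each of two sections and a different list. Treatments and assessments are unchanged. The downside is some predictability near the end of a block in an unblinded single-site trial, limited by mixed block sizes and concealment.

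If simple randomization is kept, sections 9.4 and 11.2 should stop presenting 13 and 10 per group as properties of the design, and should give the expected spread of arm sizes instead.

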##### **Treatment Visit (Day 0) (may be the same day as screening visit):**

- Subjects will complete the Defense and Veterans Pain Rating Scale (DVPRS) and DVPRS Supplemental Questionnaire before treatment.
- Subjects will be prescribed naproxen 220 mg BID (twice a day) #15 as standard of care treatment for pain (unless they refuse or have a contraindication for use)
- Subjects will be given treatment according to their randomization group following the Acupuncture Procedure below: Step 1: Either the left or right ear is chosen for the placement of the needles per provider or patient preference. Step 2: Needles will be placed in the following points on the chosen ear: Cingulate Gyrus, Thalmus, Omega 2, Point Zero, and Shen Men. Step 3: If the patients desires further pain reduction, acupuncture needles will be placed in the same points in the opposite ear. The maximum number of needles in each ear is 5.

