##### **Aim**

The aim of this pilot study is to conduct an unblinded pilot randomized clinical study on the effectiveness and tolerability of auricular semi-permanent (ASP) vs intradermal (long), and pyonex needles in Battlefield Acupuncture (BFA) for the treatment of pain.

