## 10.0

### Study Procedures, Data Management, and Privacy

#### 10.1 Study Procedures:

Describe step-by-step how the study will be conducted from beginning to end

Active duty members and DoD beneficiaries, age 18 years or older, meeting the inclusion/exclusion criteria will be offered an opportunity to participate. They will be recruited from the clinics located at 99MDG (Nellis AFB). All of the below items are research-related unless marked as 'standard of care':

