## 10.2 Data Collection:

Describe all the data variables, information to be collected, the source of the data, and how the data will be operationally measured.

We will measure pain utilizing the DVPRS just before BFA therapy, 10-15 minutes after, 24 hours and 7 days post-therapy. Needle Tolerance questionnaire will be administered after DVPRS 10-15 minutes after, 24 hours and 7 days post-therapy.

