# 11.0

## Statistical/Data Analysis Plan

### 11.1 Statistical Considerations:

List the statistical methods to be used to address the primary and secondary objectives, specific aims, and/or research hypotheses. Explain how missing data and outliers will be handled in the analysis. The analysis plan should be consistent with the study objectives. Include any sub-group analyses (e.g., gender or age group). Specify statistical methods and variables for each analysis. Describe how confounding variables will be controlled in the data analysis

**Outcome Measures:** There are two outcome measures. The effectiveness outcome measure is the Defense and Veterans Pain Rating Scale (DVPRS). The DVPRS [1,2] consists of an 11-point numerical rating scale with 0 indicating no pain and 10 indicating severe pain. It has been confirmed for reliability and validity in measuring both acute and chronic pain, and is currently the standard for pain measurement throughout DoD and VA health systems. The DVPRS demonstrates linear scale qualities allowing parametric methods to be used. There will be four repeated measurements of the DVPRS: pre-acupuncture, post-acupuncture, 24 hours and one week post-therapy. The needle tolerance outcome will be measured using an in-house developed questionnaire. It employs 5-point ordinal scales to evaluate 12 post-therapy experiences or perception encompassing adverse outcomes, inconveniences, and satisfaction. There will be three repeated measurements: post-acupuncture, 24 hours and 1 week post-therapy.

**Missing Data and Outliers:** Outliers will be checked for clerical error. If improperly recorded, the data will be corrected, and, if found to be properly recorded, will be retained. Medians, means and ranges will be calculated and assessed to accommodate extreme observations. Subjects with missing data will be excluded from analysis and the estimated sample size seen below adjusted for this eventuality. Furthermore, an analysis of sample characteristics of retained and dropped subjects will be performed to determine whether bias has been introduced due to exclusion.

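### In this unblinded trial the listed order puts randomization before the only pre-treatment pain rating, so subjects may know their needle when they rate baseline (minor; free to fix)

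*Combined protocol and SAP*

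**What the plan says.** The Aim in section 9.3 is to "conduct an unblinded pilot randomized clinical study" of three needle types. The prompt for section 10.1 is "Describe step-by-step how the study will be conducted from beginning to end", so the order of its entries is the protocol's own account of the sequence.

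That sequence is:

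1. **Screening visit.** Consent, medical history, demographics, medications and a pregnancy reminder. No pain rating is listed.
2. **Randomization.** "Subjects will be randomized using a random number generator using simple randomization into 1 of 3 research treatment groups".
3. **Treatment Visit (Day 0).** The first item is "Subjects will complete the Defense and Veterans Pain Rating Scale (DVPRS) and DVPRS Supplemental Questionnaire before treatment". The naproxen prescription and then the needling follow. The heading adds that this visit "may be the same day as screening visit", so it may also be a later day.

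Section 10.2 confirms that there is a single pre-treatment score: "We will measure pain utilizing the DVPRS just before BFA therapy, 10-15 minutes after, 24 hours and 7 days post-therapy". Section 11.1 makes that score part of the outcome: "There will be four repeated measurements of the DVPRS: pre-acupuncture, post-acupuncture, 24 hours and one week post-therapy". Section 11.6 tests H01 (needle groups) and H02 (times) by a mixed-effects repeated-measures ANOVA. If a null is rejected, contrasts between and within needle and time groups follow.

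The plan does not say when the subject learns the assignment, and it describes no step that conceals the assignment until the baseline score is in.

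**The concern.** The pre-treatment score is useful as a reference because it cannot have been influenced by the arm. A self-rated score taken from someone who already knows the needle loses that property.

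The protocol itself gives reasons to expect opinions about the needles. Section 9.6 describes ASP needles as painful enough to deter patients from a second treatment, and section 9.3 hypothesizes that Pyonex is the most effective and best tolerated. Excluding needle-phobic patients (section 12.6) removes the extreme cases but not ordinary apprehension or hope.

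If one arm's baseline is shifted, any comparison of improvement between needles inherits the shift, and nothing in the planned analysis separates it from a treatment effect. A smaller, related issue arises when Day 0 falls after screening: a subject already assigned to an unwelcome needle has an opportunity not to return.

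**Working it through.** **Inputs from the documents.** Section 11.5 gives a DVPRS mean of 4.4, an SD of 2.4, a minimal clinically important difference (MCID) of a 25% change, 10 subjects per arm (30 in all), power 0.44 and alpha 0.14. Section 11.1 gives four measurements.

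**Inputs assumed.** The documents give neither the baseline shift b nor the within-subject correlation ρ. I use b = 0.25, 0.5 and 1.0 point, and ρ = 0.5 and 0.7.

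**Step 1: reproduce the plan's figure as a check on the inputs.**
- MCID = 0.25 × 4.4 = 1.1 points; d = 1.1/2.4 = 0.458; f = d/2 = 0.229.
- For the between-group test, λ = f² × N × m / (1 + (m − 1)ρ) = 0.0525 × 30 × 4 / (1 + 3 × 0.5) = 2.52.
- With 2 and 27 degrees of freedom and alpha 0.14, power is 0.442, against the stated 0.44.

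This relies on ρ = 0.5, and other combinations of f and ρ come close too. It supports the 1.1-point MCID and the SD of 2.4. It has no bearing on the order of procedures.

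**Step 2: effect of a baseline shift.** Let knowledge of the needle add b to one arm's mean pre-treatment score and nothing to its later scores.
- Between-arm contrast of (post − pre): bias of size b.
- That arm's mean over the four times, as compared under H01: moves by b/4.

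| b (points) | b as share of MCID (b/1.1) | Movement in H01 mean (b/4) | b/4 as share of MCID |
|---|---|---|---|
| 0.25 | 23% | 0.06 | 6% |
| 0.5 | 45% | 0.125 | 11% |
| 1.0 | 91% | 0.25 | 23% |

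The two effects point in opposite directions. An inflated baseline makes that arm's improvement look larger and its four-time average look worse.

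**Step 3: scale against sampling error.** For one pairwise comparison of change with 10 per arm:
- SE = 2.4 × √(2(1 − ρ)) × √(2/10), which is 1.07 points at ρ = 0.5 and 0.83 at ρ = 0.7.
- With no true difference, the chance of rejecting at a nominal two-sided 0.05 is P(Z > 1.96 − b/SE) + P(Z < −1.96 − b/SE), by normal approximation.

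| b (points) | ρ = 0.5 | ρ = 0.7 |
|---|---|---|
| 0.25 | 0.056 | 0.060 |
| 0.5 | 0.075 | 0.092 |
| 1.0 | 0.154 | 0.225 |

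These rates are for a single unadjusted contrast. They do not allow for the Holm correction or for the condition that a null must first be rejected.

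**The case against.** **Early disclosure is inferred, not documented.** The randomization entry gives the method and the three groups, but no time of assignment or disclosure. Within Day 0 the pain score is listed first, and the first step that visibly depends on the arm is the needling. A site could follow the text and still reveal the needle only after the rating. This stands. A reader might infer that baseline is rated with knowledge of the arm; the documents show only that the order allows it.

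**The baseline is not the anchor of the whole analysis.** A reader might also infer that every result is a change from baseline. The plan names no change-from-baseline endpoint and no baseline covariate. H01 compares means that include the pre-treatment score, so a shift there is diluted to b/4. The full b applies only to pre-to-post or needle-by-time contrasts, which are run only after a rejection. This stands too.

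**The size is hypothetical and may partly cancel.** No document supports any particular b. If a fraction c of the shift persists in the later ratings, the change contrast is biased by b(1 − c), which is zero when c = 1. For b up to 0.5 the bias is at most about 60% of the standard error (0.5/0.83). This is why a range is given rather than one figure.

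**Loss before treatment is a separate matter.** If screening and Day 0 coincide, there is no return visit to miss. Section 11.1 also plans a comparison of retained and dropped subjects. That is fair: limiting such loss is a side benefit of the fix and not evidence for the point.

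**The larger open-label problem remains.** Every later pain score is self-rated by someone who has received a known needle. Reordering does not change that. But the needles stay in place for minutes in one arm and for days in the others (section 10.1, Acupuncture Needles), which makes blinding hard, whereas the baseline score can be protected easily.

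**Conclusion.** The point holds as a minor one. The documents establish that the trial is unblinded, that randomization is listed before the only pre-treatment DVPRS, that the two may fall on different days, and that nothing keeps the assignment from the subject in between. They do not establish that subjects will in fact know their needle when they rate baseline, or that any shift will occur.

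Under the assumptions of a shift confined to one arm, no carry-over to later ratings, and b between 0.25 and 1.0 point, a between-arm pre-to-post or needle-by-time contrast is biased by 23% to 91% of the MCID. The H01 group mean moves by 0.06 to 0.25 point. Neither the presence nor the direction of a shift can be predicted from the documents. The case for acting rests on the remedy being nearly free, and on this pilot being meant to inform a larger multi-site trial (section 9.3, Goals) that could inherit the sequence.

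**What to change.** Reorder section 10.1 so that, on Day 0, the subject completes the DVPRS and the DVPRS Supplemental Questionnaire before the random assignment is generated or disclosed. Place randomization immediately before needling. State explicitly that neither the subject nor the person collecting the baseline forms knows the assignment at that time. Section 10.2 can then say that the pre-treatment score precedes randomization.

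The cost is an edit to the order of two steps. It adds no visit, subject or measurement and changes no treatment. It also limits arm-related loss between assignment and treatment. It does not remove expectation effects from the ratings at 10-15 minutes, 24 hours and 7 days, and the report should say so.

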##### **Post-Treatment (10-15 minutes Post Treatment) In-person:**

- Subjects will complete the DVPRS and DVPRS Supplemental Questionnaire.
- Subjects will complete the Needle Tolerance Questionnaire.

